## 12.2 Analysis Sets

Three analysis sets will be used: the Full Analysis Set (FAS), the PPAS, and the Safety Analysis Set (SafAS).

### 12.2.1 Full Analysis Set

The FAS is defined as the subset of subjects who received at least 1 dose of the study vaccine and had a valid post-vaccination serology result. All subjects will be analyzed according to the treatment group to which they were randomized.

### 12.2.2 Safety Analysis Set

The SafAS is defined as those subjects who have received at least 1 dose of the study vaccine and have any safety data available. All subjects will have their safety analyzed according to the vaccine they actually received. If the vaccine received by a subject does not correspond to any study group, the subject will be excluded from the SafAS. The corresponding safety data will be presented in separate listings.

### 12.2.3 Per-Protocol Analysis Set

The PPAS is a subset of the FAS. The subjects presenting with at least one of the following relevant protocol deviations will be excluded from the PPAS:

- Subject did not meet all protocol-specified inclusion criteria or met at least one of the protocol-specified exclusion criteria
- Subject did not receive vaccine
- Subject received a vaccine other than the one that he/she was randomized to receive
- Preparation and/or administration of vaccine was not done as per-protocol
- Subject did not receive vaccine in the proper time window
- Subject did not provide post-dose serology sample in the proper time window or a post-dose serology sample was not drawn. The time windows are defined as D30 to D44 post-vaccination.
- Subject received a protocol-prohibited Category 2 or Category 3 therapy/medication/vaccine
- Subject's serology sample did not produce a valid test result
- Subject had other protocol deviations that affected the subject's immune response, as determined by the clinical team before locking the database

#### 12.2.4 Populations Used in Analyses

All immunogenicity analyses will be performed on the PPAS. Additional immunogenicity analyses will be performed for exploratory purposes on the FAS. In the FAS, subjects will be analyzed by the vaccine group to which they were randomized.

The safety analyses will be performed on the SafAS. Subjects will be analyzed according to the vaccine they actually received.

### 12.3 Handling of Missing Data and Outliers

#### 12.3.1 Safety

No replacement will be done.

#### 12.3.2 Immunogenicity

Missing data will not be imputed. No test or search for outliers will be performed.

In order to appropriately manage extreme values (undetectable responses  $< \text{LLOQ}$  and  $\geq$  upper limit of quantitation [ $\text{ULOQ}$ ]), the following computational rule is applied to the values provided in the clinical database for each blood sample drawn for analysis purposes:

- If a value is  $< \text{LLOQ}$ , then use the computed value  $\text{LLOQ}/2$
- If a value is between  $\geq \text{LLOQ}$  and  $< \text{ULOQ}$ , then use the value
- If a value is  $\geq \text{ULOQ}$ , then use the computed value  $\text{ULOQ}$

The derived endpoint of fold-rise is computed as follows:

- Calculate the fold-rise of values as the ratio of post-baseline computed value divided by baseline computed value

If baseline or post baseline value is missing, then the seroconversion is missing.

#### 12.3.3 Efficacy

Not applicable.

### 12.4 Interim/Preliminary Analysis

No interim or preliminary analyses are planned.

### 12.5 Determination of Sample Size and Power Calculation

[Redacted]

[Redacted]

[Redacted]

[Redacted]

[Redacted]

[Redacted]

[Redacted]

[Redacted]

[Redacted]

## 13 Ethical and Legal Issues and Investigator/Sponsor Responsibilities

### 13.1 Ethical Conduct of the Trial/Good Clinical Practice

The conduct of this trial will be consistent with the standards established by the Declaration of Helsinki and compliant with the ICH guidelines for GCP as well as with all local and/or national regulations and directives.

### 13.2 Source Data and Source Documents

“Source data” are the data contained in source documents. Source documents are original documents or certified copies, and include, but are not limited to, diary cards, medical and hospital records, screening logs, informed consent/assent forms, telephone contact logs, and worksheets. The purpose of trial source documents is to document the existence of subjects and to substantiate the integrity of the trial data collected. Investigators must maintain source documents so that they are accurate, complete, legible, and up to date.

For missing or discrepant data on a diary card, the study coordinator will obtain verbal clarification from the subject, enter the response into the “Investigator’s comment” page of the DC, and transfer the information to the CRF.

The subject pre-screening log should list all individuals contacted by the Investigators to participate in the trial, regardless of the outcome.

The Investigator must printa any electronic records on an ongoing basis, sign and date them immediately after creation, and keep the printouts on file as source documents that can be verified by the Sponsor or an inspector against the electronic records. Any later changes of an electronic record require the record to be re-printed, dated (with an indication of the date of change), and signed. Such records must also be kept together with the original printed copy.

### 13.3 Confidentiality of Data and Access to Subject Records

Prior to initiation of the trial, the Investigator will sign a fully executed confidentiality agreement with Sanofi Pasteur.

Sanofi Pasteur personnel (or designates), the IECs/IRBs, and regulatory agencies, including the Food and Drug Administration (FDA), require direct access to all study records, and will treat these documents in a confidential manner.

In the event a subject’s medical records are not at the investigational site, it is the responsibility of the investigator to obtain those records if needed.

---

a Unless the electronic medical records are managed by validated computerized systems that are compliant with US 21 CFR Part 11, in which case they are acceptable on their own.

## 13.4 Monitoring, Auditing, and Archiving

### 13.4.1 Monitoring

Before the start of the trial (i.e., before the inclusion of the first subject in the first center), the Investigators and the Sponsor's staff or a representative will meet at the site-initiation visit to discuss the trial protocol and the detailed trial procedures. Emphasis will be placed on inclusion and exclusion criteria, visit timing, safety procedures, informed consent procedures, SAE reporting procedures, CRF completion, and the handling of samples and products. The Sponsor's staff or a representative will ensure and document that all material to be used during the trial has been received at the site; and that the study investigator team and local Sponsor/delegate staff have been properly informed about the trial, GCP and regulatory requirements, and the Sponsor's procedures. Specific training sessions for the study investigator team and the CRAs on these topics may be performed as necessary, and should be documented.

The following instruction manuals will be provided: the CRF Completion Guidelines for entering data into the CRF, and the Operating Guidelines for detailed trial procedures such as the product management and sample-handling procedures.

After the start of the trial, the Sponsor's staff or a representative will be in regular contact with the investigational team through telephone calls and regular follow-up visits. The Investigator or delegate must be available for these visits, and must allow the Sponsor/delegate staff direct access to subject medical files and CRFs. During these visits, the Sponsor/delegate staff will:

- Evaluate the quality of the trial progress (adherence to protocol and any study-specific guidelines, quality of data collection and document completion, signature of consent forms, occurrence of SAEs, sample and product management, cold-chain monitoring, archiving)
- Source-verify completed CRFs and any corresponding answered queries
- Determine the number of complete or ongoing issues identified at monitoring visits (e.g., protocol deviations, SAEs). Any identified problems will be discussed with the Investigator, and corrective or preventive actions will be determined, as appropriate.
- After all protocol procedures have been completed and the data have been entered into the CRF, the Investigator must still be available to answer any queries forwarded by the Sponsor. All data-related queries must be completed prior to database lock.

At the end of the trial, a close-out visit will be performed to ensure that:

- The center has all the documents necessary for archiving
- All samples have been shipped to the appropriate laboratories
- All unused materials and products have been either destroyed or returned to the Sponsor

### 13.4.2 Audits and Inspections

A quality assurance audit may be performed at any time by the Sponsor's Clinical and Medical Quality Operations department (C&MQO) or by independent auditors to verify that the trial has been conducted according to the protocol, GCP and ICH requirements, and other applicable

regulations. An inspection may be conducted by regulatory authorities. The Investigator must allow direct access to trial documents during these inspections and audits.

### **13.4.3 Archiving**

The Investigator must keep all trial documents after the completion or discontinuation of the trial, whatever the nature of the investigational center (private practice, hospital, or institution), for as long as required by applicable laws and regulations. In the absence of any applicable laws or regulations, trial documents will be kept at a minimum for the duration indicated on the Clinical Trial Agreement (CTA). In no event, should study personnel destroy or permit the destruction of any trial documents upon less than 90 days advance written notification to the Sponsor. In addition, trial documents should continue to be stored, at Sponsor's sole expense, in the event that the Sponsor requests in writing that such storage continues for a period of time that exceeds that required by any applicable law or regulation or the CTA. The Investigator will inform Sanofi Pasteur of any address change or if they will no longer be able to house the trial documents.

Archived data may be held on electronic records, provided that a back-up exists and that a hard copy can be obtained if required. The protocol, documentation, approvals, and all other documents related to the trial, including certificates attesting that satisfactory audit and inspection procedures have been carried out, will be kept by the Sponsor in the Trial Master File (TMF). Data on AEs are included in the TMF. All data and documents will be made available if requested by relevant authorities.

### **13.5 Financial Contract and Insurance Coverage**

A Clinical Trial Agreement will be signed by all the parties involved in the trial's performance, if relevant. The Sponsor has an insurance policy to cover any liabilities that may arise from use of the product and/or the study protocol.

### **13.6 Stipends for Participation**

Subjects may be provided with a stipend according to local practice to compensate for the travel costs incurred for study visits and procedures.

### **13.7 Publication Policy**

Data derived from this trial are the exclusive property of Sanofi Pasteur. Any publication or presentation related to the trial must be submitted to Sanofi Pasteur for review before submission of the manuscript. After publication of the results of the trial, any participating center may publish or otherwise use its own data provided that any publication of data from the trial gives recognition to the trial group. In addition, Sanofi Pasteur shall be offered an association with all such publications, it being understood that Sanofi Pasteur is entitled to refuse the association.

Sanofi Pasteur must have the opportunity to review all proposed abstracts, manuscripts, or presentations regarding this trial at least 90 days prior to submission for publication/presentation. Any information identified by Sanofi Pasteur as confidential must be deleted prior to submission, it being understood that the results of this trial are not to be considered confidential.

Sanofi Pasteur's review can be expedited to meet publication guidelines.

This trial will evaluate the immunogenicity and safety of a single dose of the quadrivalent Meningococcal Polysaccharide (Serogroups A, C, Y and W) Tetanus Toxoid Conjugate Vaccine (hereafter referred to as MenACYW conjugate vaccine) in toddlers 12 to 23 months of age who are either meningococcal vaccine naïve or have a background of vaccination with monovalent MenC vaccines during infancy.

The MenACYW conjugate vaccine is designed for the immunization of individuals of all ages (infants 6 weeks of age and older through and including older adults > 65 years of age) against invasive meningococcal disease (IMD). The purpose of the vaccine is to provide broad coverage against circulating meningococcal strains from serogroups A, C, Y, and W. Compared to a previous Sanofi Pasteur meningococcal vaccine, Menactra[®], the MenACYW conjugate vaccine is prepared by using tetanus toxoid as the carrier protein. Conjugation of PS antigens to a protein carrier can induce T-cell-dependent immune responses, which are anticipated to give rise to higher antibody titers, longer duration of the immune response, and enhanced immunologic memory that allows for a booster response.

The monovalent MenC conjugate vaccines are made from capsular polysaccharide that has been extracted from cultures of capsular group C *Neisseria meningitidis*. The polysaccharide is linked (conjugated) to a carrier protein, either CRM₁₉₇ (a non-toxic variant of diphtheria toxin) or tetanus toxoid. The conjugation increases the immunogenicity, especially in young children in whom the plain polysaccharide vaccines are less immunogenic. The vaccination schedule and the number of vaccinations vary across the EU countries. Depending on the country, an infant may have received 1 to 2 doses of meningococcal C conjugate vaccine during the first year of life.

The purpose of MET51 is to evaluate the quadrivalent meningococcal conjugate vaccine when used as a single-dose toddler vaccine in individuals who are either meningococcal vaccine naïve or have received one or more doses of monovalent MenC vaccines during infancy. The study will aim to demonstrate non-inferior immunogenicity of MenACYW conjugate vaccine versus Nimenrix[®] and evaluate the safety of 1 dose of MenACYW conjugate vaccine compared to 1 dose of Nimenrix[®] in toddlers 12 to 23 months of age who are either meningococcal vaccine naïve or had received monovalent MenC vaccination during infancy.

2 Trial Objectives

2.1 Primary Objectives

- 1) To demonstrate the non-inferiority of the antibody response to meningococcal serogroups A, C, Y, and W after a single dose of MenACYW conjugate vaccine or Nimenrix[®] in toddlers who

either are meningococcal vaccine naïve or have received monovalent MenC vaccination during infancy

- 2) To demonstrate the non-inferiority of the antibody response to meningococcal serogroups A, C, Y, and W after a single dose of MenACYW conjugate vaccine or Nimenrix[®] in meningococcal vaccine naïve toddlers

2.2 Secondary Objectives

- 1) To compare the antibody responses (geometric mean titers [GMTs]) to meningococcal serogroups A, C, Y, and W after a dose of MenACYW conjugate vaccine or Nimenrix[®] as measured by serum bactericidal assay using human complement (hSBA) in toddlers who either are meningococcal vaccine naïve or have received monovalent MenC vaccination during infancy
- 2) To compare the antibody responses (GMTs) to meningococcal serogroups A, C, Y, and W after a dose of MenACYW conjugate vaccine or Nimenrix[®] as measured by hSBA in meningococcal vaccine naïve toddlers
- 3) To compare the antibody responses (GMTs) to meningococcal serogroups A, C, Y, and W after a dose of MenACYW conjugate vaccine or Nimenrix[®] as measured by hSBA in toddlers who received monovalent MenC vaccination during infancy

2.3 Observational Objectives

Immunogenicity

- To describe the antibody response to meningococcal serogroups A, C, Y, and W before and 30 days (+14 days) after a dose of MenACYW conjugate vaccine or Nimenrix[®] in terms of serum bactericidal assay using baby rabbit complement (rSBA) titers $\geq 1:8$ and $\geq 1:128$ in toddlers in a subset of subjects per group:
 - Group 1 and Group 2: 100 subjects each
 - Group 3: 50 subjects in each subgroup (MenC-TT or MenC-CRM primed subjects)
 - Group 4: 25 subjects in each subgroup (MenC-TT or MenC-CRM primed subjects)
- To describe the antibody response to meningococcal serogroups A, C, Y, and W before and 30 days (+14 days) after vaccination with MenACYW conjugate vaccine in toddlers
- To describe the antibody responses to the meningococcal serogroups A, C, Y, and W before and 30 days (+14 days) after vaccination with Nimenrix[®] in toddlers
- To describe the antibody responses to the meningococcal serogroups A, C, Y, and W before and 30 days (+14 days) after vaccination with MenACYW conjugate vaccine or Nimenrix[®] in toddlers who received monovalent MenC vaccine conjugated to the tetanus toxoid carrier protein during infancy
- To describe the antibody responses to the meningococcal serogroups A, C, Y, and W before and 30 days (+14 days) after vaccination with MenACYW conjugate vaccine or Nimenrix[®] in

toddlers who received monovalent MenC vaccine conjugated to the CRM₁₉₇ protein carrier during infancy

Safety

To evaluate the safety profile of MenACYW conjugate vaccine and Nimenrix[®].

3 Description of the Overall Trial Design and Plan

3.1 Trial Design

This was a Phase III, modified double-blind, randomized, parallel-group, active-controlled, multi-center trial to compare the immunogenicity and describe the safety of a single dose of MenACYW conjugate vaccine to a single dose of a licensed quadrivalent meningococcal polysaccharide groups A, C, W-135, and Y conjugate vaccine, Nimenrix[®], in toddlers (12 to 23 months of age) in the EU who are either meningococcal vaccine naïve or received monovalent MenC vaccination during infancy.

Approximately 918 healthy toddlers aged 12 to 23 months were to be enrolled and randomized as follows depending on the meningococcal background:

Meningococcal Vaccine-Naïve Subjects: 612 subjects were to be randomized in a 1:1 ratio to the following 2 groups:

- Group 1: MenACYW conjugate vaccine (n=306)
- Group 2: Nimenrix[®] (n=306)

MenC-Primed Subjects: 306 subjects were to be randomized in a 2:1 ratio to the following 2 groups:

- Group 3: MenACYW conjugate vaccine (n=204)
- Group 4: Nimenrix[®] (n=102)

Enrollment of MenC-primed subjects was stratified by the type of primed vaccine, MenC-TT (NeisVac-C[®]) or MenC-CRM (Menjugate[®], Meningitec[®]), considering that at least 25% and a maximum of 50% of subjects had been primed with MenC-CRM as described in Table 3.1 below:

Table 3.1: MenC priming strategy

Priming	Group 3 MenACYW conjugate vaccine	Group 4 Nimenrix [®]
MenC-TT	102 - 152*	51 - 76*
MenC-CRM	52* - 102	26* - 51

Total	204	102
--------------	-----	-----

*Sample size corresponding to 25% of subjects primed with MenC-CRM

All subjects were to provide blood samples for immunogenicity assessment at baseline (pre-vaccination) and at 30 to 44 days post-vaccination.

Solicited adverse event (AE) information were to be collected for 7 days after vaccination, unsolicited AE information were to be collected from Visit (V) 01 (Day [D] 0) to V02 (D30 [+14 days]), and serious adverse event (SAE) information, [REDACTED] were to be collected throughout the trial.

3.2 Trial Plan

Eligible subjects were identified and recruited.

A schedule of assessments and study vaccinations is provided in [Table 3.2](#).

Vaccination

All subjects were to receive a single dose of either MenACYW conjugate vaccine or Nimenrix® on D0 (V01).

Blood Sampling

All subjects were to provide a pre-vaccination blood sample at V01 (D0) and a post-vaccination sample at V02 (30 to 44 days after vaccination at V01).

Collection of safety data

All subjects were to be observed for 30 minutes after vaccination and any unsolicited systemic AEs occurring during that time were to be recorded as immediate unsolicited systemic AEs in the electronic case report form (CRF)

The subjects' parent/legally acceptable representative were to record information in a diary card (DC) about solicited reactions from D0 to D07 after vaccination and unsolicited AEs only from D0 to V02 (D30 + 14 days). SAEs were reported throughout the duration of the trial.

In addition, the subject's parent/legally acceptable representative was asked to notify the site immediately about any potential SAEs at any time during the trial.

Staff contacted the subject's parent/legally acceptable representative by telephone on D08 (+2 days) to identify the occurrence of any SAE not yet reported and to remind them to complete the DC up to V02 and to bring it back to V02 (D30 + 14 days).

The completed DC was reviewed with the subject's parent/legally acceptable representative at V02 and collected at V02 (D30 + 14 days).

4 Endpoints and Assessment Methods

4.1 Primary Endpoints and Assessment Methods

See Section 9.1 of the protocol.

4.2 Secondary Endpoints and Assessment Methods

See Section 9.2 of the protocol.

4.3 Observational Endpoints and Assessment Methods

See Section 9.3 of the protocol.

4.4 Derived Endpoints: Calculation Methods

4.4.1 Safety

4.4.1.1 Solicited Reactions

4.4.1.1.1 Daily Intensity

All daily records for solicited reactions will be derived into daily intensity according to the following classification: None, Grade 1, Grade 2, Grade 3, or Missing.

For the derivation of daily intensities the following sequential steps will be applied:

- 1) Solicited reactions (except Fever) with an investigator presence recorded as “No” and with all daily records missing then all daily intensities will be derived as None.
- 2) For a temperature partially missing after decimal point, the data will be analyzed replacing “MD” (missing data) by zero. For example, a “39.MD” daily temperature will be considered as “39.0°C” at the time of analysis.
- 3) For non-measurable solicited reactions, daily intensities will correspond to daily records reported in the clinical database. For measurable solicited reactions the daily measurements reported in the clinical database will be converted based upon the intensity scales defined in the protocol; this assumes a reaction that is too large to measure (non measurable, “NM”) is Grade 3.

Note: The maximum intensity on the ongoing period is derived from the record of the maximum intensity/measurement after the end of the solicited period following the rule described above.

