4.4.1.1.2 Maximum Overall Intensity

Maximum overall intensity is derived from the daily intensities computed as described in [Section 4.4.1.1.1](#) and is calculated as the maximum of the daily intensities over the period considered.

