4.4.1.1.3 Presence

Presence is derived from the maximum overall intensity on the period considered:

- None: No presence
- Grade 1, Grade 2, or Grade 3: Presence
- Missing: Missing presence

Subjects with at least one non-missing presence for a specific endpoint will be included in the analysis. Conversely, those without a non-missing presence will not be included in the analysis of the endpoint.

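### For the eight solicited reactions other than fever, a child with no daily records is kept when presence is No but lost when presence is Yes, which can only lower a group's reported rate

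*SAP*

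**What the plan says.** SAP 4.4.1.1.1 derives daily intensity for solicited reactions in sequential steps.

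- **Step 1** applies when the investigator's entry for presence is No "and with all daily records missing then all daily intensities will be derived as None". Fever is expressly outside this step.
- **Step 2** concerns fever only: "For a temperature partially missing after decimal point, the data will be analyzed replacing" the missing decimal by zero, so that a reading of 39 with no decimal is analysed as 39.0°C.
- **Step 3** uses the daily records alone. For non-measurable reactions, "daily intensities will correspond to daily records reported in the clinical database"; for measurable ones, the recorded measurement is converted to a grade.

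The next two sections build on this. Under 4.4.1.1.2 the maximum intensity "is calculated as the maximum of the daily intensities over the period considered". Under 4.4.1.1.3, "Presence is derived from the maximum overall intensity on the period considered", and a Missing maximum gives a Missing presence. That section closes: "Conversely, those without a non-missing presence will not be included in the analysis of the endpoint".

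For missing solicited intensities, SAP 5.3.1.4 only refers back to 4.4.1.1.1. No section says what happens when the investigator recorded Yes and every daily record is missing.

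**The concern.** One field, the investigator's record of presence, settles the outcome when it says No and has no effect when it says Yes. A child known from that field to be reaction-free is counted. A child known from the same field to have reacted disappears from the analysis of that reaction.

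The case can arise. The diary is reviewed at Visit 2, 30 to 44 days after vaccination. Protocol 11.1 lets information not documented in the diary be captured in the source document and then entered in the CRF. For redness and swelling, Protocol Table 9.1 takes the grade from a measured size. A parent may remember that there was redness but not how large it was on each day.

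At stake are the percentages and 95% confidence intervals for solicited reactions, a core part of the safety description of both vaccines.

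**Working it through.** **Inputs from the documents.** Protocol Tables 9.1 and 9.2 list 3 injection site and 6 systemic solicited reactions, 9 in all. Removing fever leaves the 8 to which step 1 applies. The planned size of Group 1 or Group 2 is 306. The documents give no rate of blank diaries and no figure on this point to reproduce.

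**Tracing a child with all daily records missing (non-fever reaction).**

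| Investigator presence | Daily intensities | Maximum | Presence | In the analysis? |
|---|---|---|---|---|
| No | None (step 1) | None | No presence | Yes, as a non-event |
| Yes | Missing (step 3, nothing recorded) | Missing | Missing | No |

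**Direction.** Let n children have daily records, x of them with the reaction. Let y have blank records with Yes, and b blank records with No.

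- Rate under the SAP: x/(n+b)
- Rate using the flag both ways: (x+y)/(n+b+y)
- Second minus first: y(n+b−x) / [(n+b)(n+b+y)]

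Since x cannot exceed n, this is never negative. It is zero only if y = 0 or every counted child reacted. A check of 59,895 combinations (n from 1 to 30, x from 0 to n, y and b from 0 to 10) found none in which the SAP rate was the higher.

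With assumed counts n = 490, x = 196, y = 8, b = 12:

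- SAP rule: 196/502 = 39.0%
- flag used both ways: 204/510 = 40.0%
- both kinds of blank dropped: 196/490 = 40.0%

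In this example the shortfall comes from the one-sided use of the flag; dropping both kinds of blank would not cause it.

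**Size (assumed).** If a fraction m of children with the reaction have Yes and no daily records, and all children without the reaction are counted, the reported rate is p(1−m)/(1−pm).

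| True rate p | m = 2% | m = 5% | m = 10% |
|---|---|---|---|
| 10% | 9.8% | 9.5% | 9.1% |
| 40% | 39.5% | 38.8% | 37.5% |
| 60% | 59.5% | 58.8% | 57.4% |

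At p = 40% in a group of 306, the number of known reactors lost is 306 × 0.40 × m, or about 2, 6 and 12.

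**Between vaccines.** With a true 40% in both groups, m = 5% in both gives a difference of 0.00 points. With m = 5% in one group only, it is −1.22 or +1.22 points, depending on which group.

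**Fever incidence.** With step 1 switched off, both kinds of blank drop out and the rate is x/n. It lies below or above the full rate according to whether Yes is more or less common among blank diaries than among recorded ones. No direction is fixed.

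**Fever grade (step 2).** In Protocol Table 9.2, Grade 2 starts above 38.5°C and Grade 3 above 39.5°C. A reading of 38 with no decimal always becomes Grade 1, though 4 of the 10 possible decimals (.6 to .9) are Grade 2. A reading of 39 always becomes Grade 2, though 4 of 10 are Grade 3. Presence of fever is never affected: 37 with any decimal is below 38.0, and 38 with any decimal is at or above it.

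**The case against.** The strongest reply is that the case should hardly occur. Under Protocol 13.2, for missing diary data "the study coordinator will obtain verbal clarification from the subject" and passes the answer to the CRF, which tends to fill blanks. Protocol 11.1 and 11.2 add interviews, required explanations for missing information, and queries. Step 1 may simply reflect a form on which No needs no daily entries while Yes does. The CRF is not among the documents, so this can be neither confirmed nor excluded. It stands as a reason to expect few such children. It does not supply the missing rule, and verbal clarification weeks later may yield a Yes without daily sizes.

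A second reply is that the SAP ranks records above flags: 4.4.1.1.7 sets aside the investigator's ongoing flag in favour of the measurement. But step 1 does use the presence flag, so the ranking is not applied consistently here. The reply does show that any remedy must be confined to children with no daily records, so that a Yes never overrides days recorded as None.

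Third, a shift of 1.2 points (p = 40%, m = 5%) is small beside the 95% interval for 40% of 306, roughly ±5.5 points (1.96 × √(0.4 × 0.6/306)). That is fair as to practical weight, though a derivation rule that pushes one way is not sampling error.

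Nor is the SAP uniformly cautious elsewhere. Missing causality is taken as related, but a missing immediate-event field is taken as not immediate (5.3.1.1 and 5.3.1.2). The case therefore rests on the asymmetry alone.

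**Conclusion.** The point holds for the eight non-fever reactions and for each group's own rate. The one-sided use of the flag lowers that rate, or leaves it unchanged if no such child exists. The exclusion follows from reading 4.4.1.1.1 to 4.4.1.1.3 together; no sentence states it. It applies only when all daily records are missing, since a single graded day makes the child a case. The size rests entirely on the assumed m. At a true 40% it is 0.5 to 2.5 points for m of 2% to 10%.

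A reader might infer more than this, in three ways that the documents do not support:

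- **That every solicited rate, fever included, is biased low.** Fever is exempt from step 1 and its incidence has no fixed direction.
- **That the comparison favours one vaccine.** The difference can move either way or not at all, and the parent and Investigator are blinded (Protocol 6.4).
- **That a trial conclusion is at risk.** Solicited reactions are observational endpoints, described without a test (SAP 5.1.3). There is no primary or secondary safety objective.

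The temperature rule is a secondary point. It can only under-grade, and only for readings of 38 and 39 without a decimal.

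**What to change.** Add to SAP 4.4.1.1.1 and 4.4.1.1.3:

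> For solicited reactions except fever, if investigator presence is Yes and all daily records are missing, presence = Yes and maximum intensity = Missing; the subject is counted in the numerator and denominator for any reaction and shown in a grade-missing row.

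Report the number of such children per group, so that the reader can see whether the rule mattered.

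For temperatures of 38 or 39 with the decimal missing, count fever as present and show the grade of that reading as missing. Assigning the highest compatible grade is not a better answer: if the ten decimals are equally likely, it would over-grade 60% of these readings, against the 40% now under-graded.

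The cost is a short SAP edit and a small programming change, a few grade-missing rows in the tables, and slightly higher reported rates if such children exist.
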